10.1.8. Study and Site Closure

The Sponsor reserves the right to terminate the study, or terminate an investigational site's participation in the study, at any time. Should Sponsor or designee, and/or the Investigator discover conditions during the course of the study that indicate that it should be discontinued, an appropriate procedure for termination will be instituted. Reasons for study or site termination include the following:

1. Investigator noncompliance with the protocol, Good Clinical Practice (GCP), or regulatory requirements
2. Unsatisfactory enrollment with respect to quantity or quality
3. Incomplete data collection; inaccurate or knowingly false data submission
4. The Principal Investigator is no longer capable of performing the tasks of the principal investigator, and no replacement can be found.
5. The DSMC determines that termination of the study is in the best interest of the research participants.
6. The Sponsor, Investigator, or IRB/IEC determines that continuation of the study will not serve any scientific purpose.

7. Circumstances beyond the control of the Sponsor or Investigator make it unreasonable to require the study's continuation.
8. A request to discontinue the study by a regulatory or health authority

10.1.9. Publication Policy

The results of this study may be published or presented at scientific meetings. If this is foreseen, the Investigator agrees to submit all manuscripts or abstracts to the Sponsor before submission. This allows the Sponsor to protect proprietary information and to provide comments.

The Sponsor will comply with the requirements for publication of study results. In accordance with standard editorial and ethical practice, the Sponsor will generally support publication of multicenter studies only in their entirety and not as individual site data. In this case, a coordinating Investigator will be designated by mutual agreement.

Authorship will be determined by mutual agreement and in line with International Committee of Medical Journal Editors authorship requirements.

10.2. CLINICAL LABORATORY TESTS

Table 2 summarizes the efficacy endpoints that will be determined from 24-hour and spot urine collections.

Table 2: Efficacy Measures Determined from Urine

Laboratory Assessments	Parameters
24-Hour urine	urinary oxalate excretion urinary creatinine excretion urinary oxalate-to-creatinine ratio urinary citrate urinary calcium urinary phosphate urinary magnesium
Spot urine	urinary oxalate excretion urinary creatinine urinary oxalate-to-creatinine ratio

The tests detailed in **Table 3** will be performed by the central laboratory, with the exception of urine pregnancy testing, which may be performed locally. Testing associated with close monitoring of liver function (as described in Section 7.1.1) may be performed at a local laboratory should the participant reside at a distance remote from the study site.

Protocol-specific requirements for inclusion or exclusion of participants are detailed in Section 5 of the protocol.

Additional tests may be performed at any time during the study as determined necessary by the Investigator or required by local regulations.

Table 3: Protocol-Required Safety Laboratory Assessments

Laboratory Assessments	Parameters	
Hematology	Red blood cell count: hemoglobin hematocrit platelet count mean platelet volume (MPV) reticulocytes mean corpuscular volume (MCV) mean corpuscular hemoglobin (MCH) mean corpuscular hemoglobin concentration (MCHC)	White blood cell count: lymphocytes, absolute and % monocytes, absolute and % eosinophils, absolute and % basophils, absolute and % neutrophils, absolute and %
Clinical Chemistry	alanine aminotransferase (ALT) aspartate aminotransferase (AST) glutamate dehydrogenase (GLDH) gamma-glutamyl transferase (GGT) alkaline phosphatase (ALP) bilirubin (total and direct) lactate dehydrogenase (LDH) total protein albumin	creatine kinase sodium chloride potassium creatinine blood urea nitrogen (BUN) cystatin C in participants < 18 years of age plasma oxalate (only in adults after Screening)
Complement	total complement hemolytic activity (CH50), C3, C4, C3a, C4a, C5a, and Bb (Note: testing not required in participants aged < 18 years)	
Coagulation Parameters	activated partial thromboplastin time (aPTT), prothrombin time (PT), international normalized ratio (INR)	
Cytokines *	epidermal growth factor (EGF), IFN- α , IFN- γ , IL-1 α , IL-1 β , IL-2, IL-4, IL-6, IL-8, IL-10, monocyte chemoattractant protein-1 (MCP-1), tumor necrosis factor alpha (TNF- α), vascular endothelial growth factor (VEGF) (Note: testing not required in participants aged < 18 years)	
Vitamin B6	collected only in participants aged \geq 18 years who are taking vitamin B6 supplements	
Routine Urinalysis	Specific gravity pH, glucose, protein, blood, ketones, bilirubin, urobilinogen, nitrite, leukocyte esterase by dipstick Microscopic examination (if blood or protein is abnormal)	
Pregnancy testing	Serum or urine human chorionic gonadotropin (hCG) pregnancy test (WOCBP)	
Antibodies	
 • Antidrug antibodies (samples will be tested when an assay is available) • Anti-double-stranded DNA antibodies 	
Other Screening Tests	
 • Follicle-stimulating hormone (as needed in postmenopausal women of non-childbearing potential only) • Urine drug screen: to include at minimum: amphetamines, barbiturates, cocaine, opiates, and benzodiazepines (not required in participants \leq 12 years of age) • Serology (HIV 1 and 2 antibodies, HBsAg, and hepatitis C virus antibody) - If tested in the past 3 months, medical record documentation of this testing may be used. Testing not required in participants < 18 years of age. 	

Investigators must document their review of each laboratory safety report.

* Note that cytokine reports will not require Investigator review due to the extended turn-around time for results.

10.3. ADVERSE EVENTS: DEFINITIONS AND PROCEDURES FOR RECORDING, EVALUATING, FOLLOW-UP, AND REPORTING

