6.3. MEASURES TO MINIMIZE BIAS: RANDOMIZATION AND BLINDING

This is a double-blind study in which treatment assignment will be blinded for the Investigators and any personnel (other than the unblinded pharmacist or designee) involved with the study conduct or evaluation at the investigational sites, the CRO, and the Sponsor.

All participants will be centrally assigned to randomized study intervention using an Interactive Web Response System (IWRS). Before the study is initiated, the log in information and directions for the IWRS will be provided to each site.

The randomization scheme will only be disclosed to selected personnel to ensure correct preparation of the study drug, correct set-up of the IWRS, safety monitoring by the DSMC, and expedited adverse reaction reporting. All aspects of blinding and unblinding for the study is outlined in the study-specific Blinding and Unblinding Plan.

Unblinding, i.e., breaking the code for an individual patient during the study, is restricted to emergency situations and should only be used under circumstances where knowledge of the treatment is necessary for the proper handling of the participant. The decision to break the code must be made by the Investigator. The study monitor and Sponsor must be informed about the code break as soon as possible. Detailed unblinding procedures are provided in a separate IWRS manual.

As DCR-PHXC is colorless to pale-yellow, an unblinded pharmacist or designee will prepare the syringes for delivery to the Investigator. To prevent any blinded site staff or study participants

from visually observing color differences between DCR-PHXC and placebo, syringes will be tinted or shrouded to mask the color difference.

Results of on-treatment 24-hour Uox measurements will not be returned to the Investigator prior to closure of the study, so as not to potentially unblind the study.

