7. STUDY INTERVENTION DISCONTINUATION AND PARTICIPANT DISCONTINUATION/WITHDRAWAL

7.1. DISCONTINUATION OF STUDY INTERVENTION

Study intervention for an individual participant may be permanently discontinued at any time at the discretion of the Investigator.

Study intervention for an individual participant must be temporarily interrupted and may be permanently discontinued for the following, as determined by the DSMC:

- any severe AE possibly, probably, or definitely related to study intervention

Study intervention for an individual participant will be permanently discontinued for any of the following:

- any SAE possibly, probably or definitely related to study intervention
- any of the changes in hepatic function detailed in Section 7.1.1
- pregnancy, as detailed in Section 10.4

Re-challenge with study intervention is not allowed.

Discontinuation from study intervention does not mean discontinuation from the study.

Remaining visits and study procedures should be completed as indicated by the SoA.

Additionally, participants in whom study intervention is prematurely discontinued will be followed until Uox returns to $\geq 80\%$ of baseline. Hematology, clinical chemistry, urinalysis, and pregnancy testing (as detailed in **Table 3**) and 24-hour urine collections will be repeated monthly. Should this follow-up take more than 6 months, participants will be re-consented for additional follow-up.

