8.5. PHARMACOKINETICS

8.5.1. Plasma Pharmacokinetics

Blood samples will be collected for measurement of plasma concentrations of DCR-PHXC and its metabolites, as specified in the SoA. Instructions for the collection and handling of biological samples will be provided in the Central Laboratory Manual. The actual date and time (24-hour clock time) of each sample will be recorded. Drug concentration information that would unblind the study will not be reported to investigative sites or blinded personnel until the study has been unblinded.

Pharmacokinetic parameters to be determined may include clearance (CL) and volume of distribution (V) estimates, along with secondary parameters of area under the concentration curve (AUC), maximum observed concentration (C_{max}), minimum observed concentration (C_{min}), time to maximum concentration (T_{max}), and terminal elimination half-life (t_{1/2}). The population PK parameters will be reported separately from the study.

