### 3.6. Blinding and Unblinding

This is a double-blind study in which treatment assignment will be blinded for investigators and any personnel involved with study conduct, evaluation at the investigational sites, [REDACTED], or the sponsor.

The randomization scheme will only be disclosed to select personnel to ensure correct preparation of the study drug, correct set-up of the IWRS, correct safety monitoring by the DSMC, and expedited adverse reaction reporting. All aspects of blinding and unblinding for the study (including possible interim analysis, emergency unblinding, unblinding following database lock) is outlined in the study-specific Blinding and Unblinding Plan.

Emergency unblinding, i.e., breaking the code for an individual patient during the study, is restricted to emergency situations and should only be used under circumstances where knowledge of the treatment is necessary for the proper handling of the participant. The decision to break the code must be made by the investigator. The study monitor and sponsor must be informed about the code break as soon as possible.

Results of on-treatment 24-hour Uox measurements will not be revealed to the investigator, sponsor or blinded study team members prior to data base lock, so as not to potentially unblind the study. Details of the ongoing quality review of 24-hour Uox measurements by the unblinded members of the study team are outlined in the Unblinded Data Review and Sample Tracking Plan.

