#### 9.4. Clinical Laboratory Evaluations – Urinalysis

All safety laboratory results obtained from 24 hour urinalysis which do not meet the completeness criteria described in section 6.1.5.2 will be set to missing in the descriptive summary tables. These safety urinalysis tests will include:

- 24 Hour Urinary Creatinine
- 24 Hour Urinary Oxalate to Creatinine Ratio
- 24 Hour Urinary Calcium
- 24 Hour Urinary Magnesium
- 24 Hour Urinary Phosphate
- 24 Hour Urinary Citrate Excretion Rate
- 24 Hour Urinary Citrate

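### On-treatment plasma oxalate in adults sits in the safety panel that investigators must review, and neither the Protocol nor the SAP says it is masked

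*Protocol*

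**What the plan says.** **What is withheld.** Protocol 6.3: "Results of on-treatment 24-hour Uox measurements will not be returned to the Investigator prior to closure of the study". SAP 3.6 widens the audience: "Results of on-treatment 24-hour Uox measurements will not be revealed to the investigator, sponsor or blinded study team members prior to data base lock". Protocol 8.5.1 adds: "Drug concentration information that would unblind the study will not be reported to investigative sites or blinded personnel". For everything else Protocol 6.3 points to another document: "All aspects of blinding and unblinding for the study is outlined in the study-specific Blinding and Unblinding Plan". SAP 3.6 makes the same reference. That plan is not among the documents reviewed.

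**What goes to the investigator.** Protocol 10.2, Table 3, is the list of required safety laboratory tests. Its clinical chemistry row includes "plasma oxalate (only in adults after Screening". The note below it reads: "Investigators must document their review of each laboratory safety report". Protocol 8.2.4 repeats the duty to review and document. The only carve-out is for cytokine reports, and the reason given is slow turn-around, not blinding.

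**What plasma oxalate is.** Protocol 8.6 names urinary oxalate, plasma oxalate and the urinary oxalate-to-creatinine ratio as the study's pharmacodynamic parameters. SAP 6.1.4 places percent change in plasma oxalate third in the hierarchical sequence.

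**Follow-up.** Protocol 7.1: "participants in whom study intervention is prematurely discontinued will be followed until Uox returns to" at least 80% of baseline. Protocol 6.7, 7.1.1 and 7.2 apply the same threshold to those who do not roll over, stop for liver findings, or withdraw.

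**The concern.** Protocol 6.3 withholds 24-hour Uox because seeing it could unblind the study. Plasma oxalate belongs to the same pharmacodynamic group, so the same reasoning applies unless the plan explains why not. Instead, the stated review rule sends it to the blinded investigator.

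Several outcomes depend on the judgement of that investigator or site. They are adverse-event causality (Protocol 10.3.4), stone events such as colic treated with medication (8.1.6.1), staff-administered quality-of-life surveys (8.1.7), and permanent discontinuation at the investigator's discretion (7.1). If site staff form a view of the arm, these can shift in ways that no analysis can later remove.

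A second, smaller issue is that the length of post-treatment follow-up is a visible function of Uox. No section says who applies the rule or how sites stay blind to its outcome.

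**Working it through.** No figure in the plan depends on this point, so there is nothing to reproduce first. The main check sets the sections side by side.

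| Result | Where listed | Stated as withheld? | Stated route to the investigator? |
|---|---|---|---|
| 24-hour Uox, on treatment | Protocol 10.2, Table 2 (efficacy) | Yes: Protocol 6.3, SAP 3.6 | No |
| Drug concentration | Protocol 8.5.1 | Yes: same section | No |
| Plasma oxalate, adults after Screening | Protocol 10.2, Table 3 (safety) | No statement | Yes: Protocol 8.2.4 and 10.2 |
| Spot-urine oxalate; oxalate-to-creatinine ratios | Protocol 10.2, Table 2 (efficacy) | No statement | None stated |
| Uox after treatment has stopped | Protocol 6.7, 7.1, 7.1.1, 7.2 | No statement | None stated, but it sets follow-up length |

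Plasma oxalate is the only row with no stated masking and a stated route to the blinded site.

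**Exposure.** The Schedule of Activities marks plasma oxalate on Days 1, 30, 60, 90, 120, 150 and 180. Day 1 is drawn before dosing and is baseline, which leaves six post-baseline visits (30, 60, 90, 120, 150, 180). Participants aged 6 to 17 have none after Screening.

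**How revealing is one value?** An answer needs the expected change on treatment and the SD of that change. The documents give neither. Entry requires plasma oxalate of no more than 30 µmol/L and eGFR of at least 30, so the room for change is also unknown.

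**How revealing is follow-up length?** This can be illustrated.

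- Inputs from Protocol 9.2: active AUC 3600 (a 40% fall over 90 days), placebo AUC 0, effect size 1.2, allocation 2:1.
- Implied SD: 3600 / 1.2 = 3000 AUC units; 3000 / 90 = 33.3 percentage points.
- Assumptions: percent change is normal, and Uox is checked while the treatment effect persists. The SD of 33.3 belongs to a 90-day average and a single collection may differ, so 20 to 45 is shown as a range.
- Threshold of 80% of baseline, i.e. a change of −20 or higher. Placebo: P = Φ(20/33.3) = Φ(0.60) = 0.726. Active: P = 1 − Φ((−20 + 40)/33.3) = 1 − Φ(0.60) = 0.274.
- Before any observation, P(active) = 2/3 = 67%.
- Follow-up continues: P(active) = 2(1 − 0.274) / [2(1 − 0.274) + (1 − 0.726)] = 1.452 / 1.726 = 84%.
- Follow-up ends at once: P(active) = 2(0.274) / [2(0.274) + 0.726] = 0.548 / 1.274 = 43%.

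| Mean fall on active | SD (points) | P(active) if continues | P(active) if ends at once |
|---|---|---|---|
| 40% (Protocol 9.2) | 33.3 | 84% | 43% |
| 40% | 20 to 45 | 80 to 91% | 27 to 49% |
| 67% (earlier single-dose study, Protocol A.7) | 33.3 | 87% | 18% |
| 67% | 20 to 45 | 84 to 93% | 2 to 31% |

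The rule shifts the odds, more so under the larger effect, but in none of these cases does it identify the arm with certainty.

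**The case against.** The strongest reply is that blinding detail has been placed elsewhere. The Blinding and Unblinding Plan is said to cover it fully, SAP 3.6 cites a further plan for unblinded data review, and Protocol 8.1.5 sends plasma oxalate sample handling to the Central Laboratory Manual. Plasma oxalate also has its own row in the Schedule of Activities, apart from serum chemistry, so the laboratory may report it separately. This stands as a limit on the claim: absence of masking cannot be shown. It does not remove the problem. If the unseen plan masks the value, it conflicts with the review duty that sites read in Protocol 8.2.4 and 10.2.

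Controls also narrow the route to bias. Vitamin B6 dose must stay stable (Protocol 5.2, 6.5), fluid intake is to be consistent and is reported (8.2.7), stone number and size are read centrally (8.1.6.2), and urine collections face creatinine and duration checks (8.1.1.1.1). The primary endpoint is a laboratory value. This also stands, and it is why the concern centres on judgement-based outcomes.

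Three stronger readings are tempting, and the documents do not support them.

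- A reader might infer that sites receive the urine ratios, because SAP 9.4 lists "24 Hour Urinary Oxalate to Creatinine Ratio" among safety urinalysis tests, next to 24-hour creatinine, and ratio times creatinine gives back the masked oxalate. But SAP 9.4 governs how incomplete collections are treated in summary tables, not what sites see, and Protocol Table 2 classes the ratios and spot oxalate as efficacy measures.
- A reader might see a flat contradiction between Protocol 6.3 and the follow-up rule. The masking covers on-treatment results only, whereas the rule uses Uox after dosing has stopped. The conflict is partial: the operator of the rule is unstated.
- A reader might conclude that follow-up length reveals the arm. The calculation shows that it informs without identifying. For completers who do not roll over, it acts after Day 180, outside the primary window.

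**Conclusion.** The gap for plasma oxalate is real on the text. A pharmacodynamic marker that is also a tested secondary endpoint is routed to blinded investigators, with no stated exemption, for every adult at up to six post-baseline visits. It should be corrected, because it can be closed cheaply and its effect on judgement-based outcomes could not be repaired afterwards.

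It would go too far to say that the blind is broken or that treatment can be deduced from plasma oxalate. The documents give no basis for sizing that, and the conclusion assumes that the separate blinding plan adds no protection. The follow-up issue is secondary. It reaches only those who stop, withdraw or do not roll over. Under the protocol's own assumptions it moves the probability of active treatment from 67% to about 84%, or down to about 43%.

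**What to change.** 1. **Protocol 6.3 and SAP 3.6:** extend the masking to on-treatment plasma oxalate and, for completeness, to spot-urine oxalate and the oxalate-to-creatinine ratios. If the Blinding and Unblinding Plan already does this, cite the provision.
2. **Protocol 10.2 and 8.2.4:** exempt post-screening plasma oxalate from investigator-facing reports and from the review duty. A footnote to Table 3 is safer than deleting the entry, because Protocol 6.7, 7.1 and 7.2 use Table 3 to define follow-up chemistry. Extend the exemption to any local laboratory used under Appendix A.4.
3. **Alerts:** route any plasma oxalate alert through unblinded personnel.
4. **Follow-up:** reconcile Protocol 6.3 and SAP 3.6 with Protocol 6.7 and 7.1 to 7.2. State that unblinded personnel run the Uox-based follow-up, and what sites are told. The follow-up rule itself is not in question here.

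The cost is a laboratory reporting setting and some wording. The downside is that the remit of the unblinded personnel must be widened: as documented it covers urinary creatinine (Protocol 8.1.1.1.1) and the quality of 24-hour Uox (SAP 3.6), not plasma oxalate. If the separate plan already masks these values, only the Protocol and SAP text changes.

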10.3.1. Definition of Adverse Event (AE)

AE Definition

 An AE is any untoward medical occurrence in a patient or clinical study participant, temporally associated with the use of study intervention, whether or not considered related to the study intervention. NOTE: Therefore, an AE can be any unfavorable and unintended sign (including an abnormal laboratory finding), symptom, or disease (new or exacerbated) temporally associated with the use of study intervention.
Events Meeting the AE Definition

 Any abnormal laboratory test results or other safety assessments (e.g., ECG, radiological scans, vital signs measurements), including those that worsen from baseline, considered clinically significant in the medical and scientific judgment of the Investigator (i.e., not related to progression of underlying disease). Exacerbation of a chronic or intermittent pre-existing condition, including either an increase in frequency and/or intensity of the condition. New conditions detected or diagnosed after study intervention administration even though it may have been present before the start of the study. Signs, symptoms, or the clinical sequelae of a suspected drug-drug interaction. Signs, symptoms, or the clinical sequelae of a suspected overdose of either study intervention or a concomitant medication. Overdose per se will not be reported as an AE/SAE unless it is an intentional overdose taken with possible suicidal/self-harming intent. Such overdoses should be reported regardless of sequelae. “Lack of efficacy” or “failure of expected pharmacological action” will not be reported as an AE or SAE. Such instances will be captured in the efficacy assessments. However, the signs, symptoms, and/or clinical sequelae resulting from lack of efficacy will be reported as AE or SAE if they fulfill the definition of an AE or SAE.
Events NOT Meeting the AE Definition

 Any clinically significant abnormal laboratory findings or other abnormal safety assessments that are associated with the underlying disease, unless judged by the Investigator to be more severe than expected for the participant’s condition. Medical or surgical procedure (e.g., endoscopy, appendectomy); the condition that leads to the procedure is the AE. Situations in which an untoward medical occurrence did not occur (social and/or convenience admission to a hospital).

- Anticipated day-to-day fluctuations of pre-existing disease(s) or condition(s) present or detected at the start of the study that do not worsen.

